8.2.1. Myelosuppression Related Events (due to disease or leukemia therapy)

- 8.2.1.1. febrile or infection episodes not requiring management in the intensive care unit

8.2.1.2. epistaxis or bleeding except for catastrophic CNS or pulmonary hemorrhage

8.2.1.3. anemia, neutropenia, lymphopenia, thrombocytopenia, leukopenia

8.2.2. Disease Related Events

8.2.2.1. symptoms associated with anemia

8.2.2.2. fatigue

8.2.2.2.1. weakness

8.2.2.2.2. shortness of breath

8.2.2.3. electrolyte abnormalities (sodium, potassium, bicarbonate, CO₂, magnesium)

8.2.2.4. chemistry abnormalities (LDH, phosphorus, calcium, BUN, protein, albumin, uric acid, alkaline phosphatase, glucose)

8.2.2.5. coagulation abnormalities

8.2.2.6. disease specific therapy (induction, maintenance, salvage, or stem cell therapy)

8.2.2.7. alopecia

8.2.2.8. bone, joint, or muscle pain

8.2.2.9. liver function test abnormalities associated with infection or disease progression

8.2.2.10. disease progression

8.2.2.11. abnormal hematologic values

8.2.3. General Therapy Related Events

8.2.3.1. catheter related events

8.2.3.2. renal failure related to tumor lysis syndrome or antibiotic/ antifungal therapy

8.2.3.3. rash related to antibiotic use

8.2.3.4. Hospitalization for the management of any of the above expected events

8.3. Abnormal hematologic values will not be recorded on the case report form. For abnormal chemical values, the apogee or nadir (whichever is appropriate) will be reported per course on the case report form.

8.4. **Serious Adverse Event Reporting (SAE)**

An adverse event or suspected adverse reaction is considered “serious” if, in the view of either the investigator or the sponsor, it results in any of the following outcomes:

- Death
- A life-threatening adverse drug experience – any adverse experience that places the patient, in the view of the initial reporter, at immediate risk of death from the adverse experience as it occurred. It does not include an adverse experience that, had it occurred in a more severe form, might have caused death.
- Inpatient hospitalization or prolongation of existing hospitalization
- A persistent or significant incapacity or substantial disruption of the ability to conduct normal life functions.
- A congenital anomaly/birth defect.

Important medical events that may not result in death, be life-threatening, or require hospitalization may be considered a serious adverse drug experience when, based upon appropriate medical judgment, they may jeopardize the patient or subject and may require medical or surgical intervention to prevent one of the outcomes listed in this definition. Examples of such medical events include allergic bronchospasm requiring intensive treatment in an emergency room or at home, blood dyscrasias or convulsions that do not result in inpatient hospitalization, or the development of drug dependency or drug abuse (21 CFR 312.32).

- Important medical events as defined above, may also be considered serious adverse events. Any important medical event can and should be reported as an SAE if deemed appropriate by the Principal Investigator or the IND Sponsor, IND Office.
- All events occurring during the conduct of a protocol and meeting the definition of a SAE must be reported to the IRB in accordance with the timeframes and procedures outlined in “The University of Texas M. D. Anderson Cancer Center Institutional Review Board Policy for Investigators on Reporting Unanticipated Adverse Events for Drugs and Devices”. Unless stated otherwise in the protocol, all SAEs, expected or unexpected, must be reported to the IND Office, regardless of attribution (within 5 working days of knowledge of the event).
- **All life-threatening or fatal events**, that are unexpected, and related to the study drug, must have a written report submitted within **24 hours** (next working day) of knowledge of the event to the Safety Project Manager in the IND Office.

- Unless otherwise noted, the electronic SAE application (eSAE) will be utilized for safety reporting to the IND Office and MDACC IRB.
- Serious adverse events will be captured from the time of the first protocol-specific intervention, until 30 days after the last dose of drug, unless the participant withdraws consent. Serious adverse events must be followed until clinical recovery is complete and laboratory tests have returned to baseline, progression of the event has stabilized, or there has been acceptable resolution of the event.

Additionally, any serious adverse events that occur after the 30 day time period that are related to the study treatment must be reported to the IND Office. This may include the development of a secondary malignancy.

Reporting to FDA:

Serious adverse events will be forwarded to FDA by the IND Sponsor (Safety Project Manager IND Office) according to 21 CFR 312.32.

It is the responsibility of the PI and the research team to ensure serious adverse events are reported according to the Code of Federal Regulations, Good Clinical Practices, the protocol guidelines, the sponsor's guidelines, and Institutional Review Board policy.

8.5. Annual Reports

If the FDA has granted an IND number, it is a requirement of 21 CFR 312.33, that an annual report is provided to the FDA within 60-days of the IND anniversary date. 21 CFR 312.33 provides the data elements that are to be submitted in the report. The Annual Report should be filed in the study's Regulatory Binder, and a copy provided to Celgene Corporation as a supporter of this study as follows.

Celgene Corporation

Attn: Medical Development

[name]

[name]

[contact]

8.6. Pregnancies:

Pregnancy of a female subject or the female partner of a male subject occurring while the subject is on azacitidine or within 28 days after the subject's last dose of Azacitidine are considered expedited reportable events. If the subject is on Azacitidine, it is to be discontinued immediately. The pregnancy must be reported to Celgene Drug Safety within 24 hours of the Investigator's knowledge of the pregnancy by facsimile using the SAE Form.

The Investigator will follow the pregnant female until completion of the pregnancy, and must notify Celgene Drug Safety of the outcome as specified below. The Investigator will provide this information as a follow-up to the initial SAE.

If the outcome of the pregnancy meets the criteria for immediate classification as a SAE (i.e., spontaneous abortion [any congenital anomaly detected in an aborted fetus is to be documented], stillbirth, neonatal death, or congenital anomaly), the Investigator should follow the procedures for Expedited Reporting of SAEs to Celgene (i.e., report the event to Celgene Drug Safety by facsimile within 24 hours of the Investigator's knowledge of the event).

Any suspected fetal exposure to Azacitidine must be reported to Celgene within 24 hours of being made aware of the event. The pregnant female should be referred to an obstetrician/gynecologist experienced in reproductive toxicity for further evaluation and counseling.

All neonatal deaths that occur within 30 days of birth should be reported, without regard to causality, as SAEs. In addition, any infant death after 30 days that the Investigator suspects is related to the in utero exposure to Azacitidine should also be reported.

In the case of a live "normal" birth, Celgene Drug Safety should be advised as soon as the information is available.

Celgene Drug Safety Contact Information:

Celgene Corporation

Drug Safety

[name]

[name]

Toll Free: [contact]

[contact]

[contact]

e-mail: [contact]

9. Statistical Considerations

9.1. This is a single arm, open label, phase I-II trial to evaluate the toxicity and efficacy of the combination of AZA and a TKI in CML patients in complete cytogenetic remission with minimal residual disease. A total of 48 patients will be accrued at a rate of 1 to 2 patients per month.

9.2. Phase I

The primary objective of phase I part is to determine the maximum tolerated dose (MTD) of AZA; and the primary endpoint is the occurrence of dose-limiting toxicity (DLT: section 4.3.3) within the first course of treatment. Standard 3+3 design will be used. The starting dose is 50 mg/m²/d x 3 days (Table 1).

Dose level	AZA (mg/m ² /d x 3 days)
-1	25
0	50
1	75

9.2.1. The 3+3 algorithm is described below:

9.2.1.1. Three patients will be enrolled at the starting dose level

9.2.1.2. If 0/3 patient experiences DLT at a given level, enroll three patients to the next higher dose level

9.2.1.3. If 1/3 patient experiences DLT at a given level, enroll additional three patients to the same dose level

9.2.1.4. If 2/3 or 2/6 patients experience DLT at a given level, the MTD has been exceeded and dose escalation will be stopped. Up to three additional patients will be enrolled at the next lower dose level if only 3 patients were treated at that level.

9.2.2. MTD is defined as the highest dose level in which 6 patients have been treated and one or fewer patient experiences DLT.

The MTD identified in phase I part will be recommended for phase II. If MTD is not determined, the highest AZA level of 75 mg/m²/d x 3 days will be used as the recommended phase II dose.

A maximum of 18 patients will be accrued for phase I part. The data from the 6 patients treated at the recommended phase II dose level (MTD or 75 mg/m²/d x 3 days if MTD is not determined) will be used in phase II part.

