3.2. Exclusion Criteria

- 3.2.1. Patients receiving any other investigational agents
- 3.2.2. Patients who are pregnant or breast-feeding
- 3.2.3. Patients with clinically significant heart disease (NYHA Class III or IV)
- 3.2.4. Known or suspected hypersensitivity to azacitidine or mannitol.
- 3.2.5. Patients with advanced malignant hepatic tumors.

4. Treatment Plan

4.1. **TKI:** Patients will continue receiving TKI at the dose they had been receiving during the last 6 months.

4.2. **AZA:**

Phase I: patients will be treated in cohorts of 3. The starting dose will be dose level 0 (50 mg/m²/d x 3 days subcutaneous or intravenous; Table 1).

4.2.1. At least 3 patients will be entered at each level. All patients treated at any one dose level must have been observed for at least four weeks before escalating to the next dose level. Patients who come off study prior to the first four weeks and have not experienced a DLT will be replaced.

Table 1: Dose escalation levels	
Dose level	AZA (mg/m ² /d x 3 days)
-3	25 (1 day only)
-2	25 (2 days only)
-1	25
0	50
1 (Target dose)	75
2	75 (for 5 days)
3	75 (for 7 days)

4.2.2. Dose escalation will be done as follows:

Dose-limiting toxicity in	Result
0/3	Escalate to next level
1/3	Enter 3 more patients
≥2/3 or ≥ 2/6	MTD exceeded. This dose level will be declared the maximally administered dose. Expand previous level to include a total of 6 patients if not already accrued to this number.

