4.2.3. Definition of Dose-Limiting Toxicity (DLT)

4.2.3.1. DLT will be defined by events that are clinically significant and possibly related to study drug occurring during the first 4 weeks (1 cycle) of therapy.

4.2.3.2. Non-hematologic DLT is defined as grade 3 or 4 toxicity (NCI common criteria, version 4.0) that is clinically significant and

considered to be at least possibly related to the study drug. Grade 3 or 4 nausea, vomiting and diarrhea will be considered DLT only if not controlled by optimal therapy.

4.2.3.3. Grade 3 biochemical abnormalities (e.g., lipase or bilirubin elevation) will only be considered DLT if accompanied by clinical consequences. Grade 3 or 4 electrolyte abnormalities will only be considered DLT if possibly related to study drug and not corrected by optimal replacement therapy.

4.2.3.4. Hematologic DLT is defined as grade ≥ 3 neutropenia and/or thrombocytopenia with a hypocellular bone marrow lasting for 6 weeks or more after the start of a course. (In case of a normocellular bone marrow, 8 weeks with pancytopenia will be considered DLT). Anemia will not be considered for the definition of DLT.

4.2.4. If dose-level 0 exceeds MTD, subsequent patients will be treated at dose level -1. Additional cohorts at lower doses (down to dose level -4) may be included if higher doses exceed MTD. If dose level -4 exceeds MTD, the study will be terminated.

4.3. **Phase II:** The dose to be used for the phase II portion of the study is $75\text{mg}/\text{m}^2$ daily for 3 days, unless MTD is defined at a lower dose level in the phase I portion of the study in which case that would become the dose to be used for the phase II portion. Other dose levels shown in Table 1 will be used for dose adjustments for toxicity or lack of improvement (as described in section 4.5.5) during therapy. For phase II portion of the study, if at any time patients need to be escalated to dose level +2 or +3, if at any time 33% or more of patients experience DLT at this dose level during the first cycle they receive at this dose, this would be considered to have exceeded MTD and that dose level should not be used any further.

4.4. Treatment with AZA (in both phase I and phase II) may be repeated every 28 days. The start of subsequent cycles may be delayed to allow for recovery of any adverse events to grade 1 or less.

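### The fallback to 75 mg/m² x 3 days in phase II does not require that this level was tested and not exceeded, and the phase I stopping rule refers to a dose level (-4) that Table 1 does not contain

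*Combined protocol and SAP*

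**What the plan says.** **Choice of phase II dose.** Section 9.2.2 gives the definition "MTD is defined as the highest dose level in which 6 patients have been treated and one or fewer patient experiences DLT" and then the fallback "If MTD is not determined, the highest AZA level of 75 mg/m²/d x 3 days will be used as the recommended phase II dose". Section 4.3 sets 75 mg/m² for 3 days as the phase II dose "unless MTD is defined at a lower dose level in the phase I portion of the study".

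**Handling of a toxic level.** Under 4.2.2, two or more DLTs in 3 or in 6 patients mean that the MTD is exceeded: "This dose level will be declared the maximally administered dose". The level below is then filled to 6. Section 4.2.4 adds three steps:

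- A mandatory step down from the starting level: "If dose-level 0 exceeds MTD, subsequent patients will be treated at dose level -1"
- An optional extension: further cohorts below that are permitted but not required, and the text takes them as far as level -4.
- A stopping rule tied to that same level: "If dose level -4 exceeds MTD, the study will be terminated"

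**The ladders.** Table 1 runs without a gap from level -3 (25 mg/m², one day) to level 3. The table in Section 9.2 has only levels -1, 0 and 1. Section 4.5.4.5.1 also names -4, as the floor for dose reductions in individual patients.

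**The concern.** The MTD definition needs 6 treated patients with at most one DLT. It can therefore go unmet for opposite reasons. Level 1 may be clean with only 3 patients treated and no higher level in Section 9, or every tested level may have been exceeded. The fallback sentence gives both outcomes the same dose. In 4.3, if no lower level qualifies, none has been defined as the MTD, so 75 stands.

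The rule that should catch the toxic outcome is incomplete. Only the step from level 0 to -1 is mandatory, and cohorts below -1 are optional. The stop is tied to a level that Table 1 does not define. If -1 is exceeded and no lower cohort is opened, no sentence says stop, while 9.2.2 names a phase II dose.

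What is at stake is the clarity of a dose-selection rule after toxicity, and a safety stop that can be applied as written.

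**Working it through.** **1. The plan's own figures.**

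- Phase I maximum: 3 levels (-1, 0, 1) x 6 = 18, as stated.
- Total: 18 + 36 - 6 = 48, as stated.
- Power: with n = 36 and rates of 5% versus 20%, the exact rule of 5 or more responders has one-sided alpha 0.0324 and power 0.873, which agrees with 87%.

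**2. The toxic outcome on the Section 9 ladder.** The documents give no expected DLT rates, so all rates here are assumed. Patients are taken as evaluable, the start is level 0, a level below an exceeded one is filled to 6, and no cohorts below -1 are opened. Write p(-1), p0 and p1 for the DLT rates at levels -1, 0 and 1.

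- D(p) = 1 - [(1-p)^3 + 3p(1-p)^2 (1-p)^3]: level exceeded under the usual 3+3 steps
- T(p) = 3p^2(1-p) + p^3: two or more DLTs in 3 added patients after 0/3
- E(p) = 1 - [(1-p)^6 + 6p(1-p)^5]: level exceeded when 6 are required

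P(no level qualifies because of toxicity) = E(p(-1)) x [D(p0) + (1-p0)^3 D(p1) T(p0)]

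The first term in the bracket covers level 0 being exceeded before level 1 is tried. The second covers level 1 being tried and exceeded first.

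| Rates at -1/0/1 | D(p0) | D(p1) | T(p0) | E(p(-1)) | Direct | Via level 1 | Total |
|---|---|---|---|---|---|---|---|
| 5/10/15% | 0.0939 | 0.1862 | 0.028 | 0.0328 | 0.0031 | 0.0001 | 0.0032 |
| 10/20/30% | 0.2914 | 0.5057 | 0.104 | 0.1143 | 0.0333 | 0.0031 | 0.0364 |
| 20/30/40% | 0.5057 | 0.6907 | 0.216 | 0.3446 | 0.1743 | 0.0176 | 0.1919 |
| 30/40/50% | 0.6907 | 0.8281 | 0.352 | 0.5798 | 0.4005 | 0.0365 | 0.4370 |

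**3. The benign outcome.** Strictly, the MTD is undetermined without toxicity when levels 0 and 1 both show 0/3: (1-p0)^3 (1-p1)^3. In the four scenarios this is 0.9^3 x 0.85^3 = 44.8%, 0.8^3 x 0.7^3 = 17.6%, 0.7^3 x 0.6^3 = 7.4% and 0.6^3 x 0.5^3 = 2.7%. Paths with 1/6 at level 0 and 0/3 at level 1 are left out, because there the wording of 9.2.2 makes level 0 the MTD.

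**4. Optional lower cohorts always opened, down to -3, with level 1 as the top.** Without the 18-patient cap, the step 2 total is multiplied by E at -2 and at -3. For 10/20/30/40/50% (levels -3 to 1) this is 0.4370 x 0.3446 x 0.1143 = 0.0172. Exact enumeration with the cap gives these results:

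| Rates at -3/-2/-1/0/1 | All levels exceeded | Cap reached first |
|---|---|---|
| 5/7.5/10/20/30% | 0.00002 | 0.0046 |
| 5/10/20/30/40% | 0.0002 | 0.0302 |
| 10/20/30/40/50% | 0.0071 | 0.1203 |

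These depend on the rates assumed below -1. With 20% and 25% at -3 and -2 in the last row, the chance that all levels are exceeded is 0.0316. Reaching the cap first is not the same as intolerance at the last level tested.

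**5. The phase II safety rule as a backstop.** With the Beta(0.4, 1.6) prior of 9.3.2, the posterior probability that the DLT rate is above 20% is 0.707 after 2/6 and 0.914 after 3/6. The rule needs more than 0.90, so it stops at 3/6. It does not stop at 2/6, a count that 4.2.2 treats as exceeded.

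**The case against.** A reader might infer that the protocol intends to treat phase II patients at 75 mg/m² after every level has failed, or that this is a likely outcome. The documents do not support either inference.

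- Section 9.2.2 calls 75 the highest level and goes on to carry forward "The data from the 6 patients treated at the recommended phase II dose level", which presupposes that the dose was given. (The count does not fit the 0/3 case, where only 3 were treated. With 6 treated and at most one DLT, the MTD would be determined.)
- Section 4.2.2 moves the team down from an exceeded level, and 4.2.4 sends patients to -1 after level 0 is exceeded. The intent to stop at the bottom of the ladder is plain despite the number.
- Section 9.3.2 stops phase II at 3/6, and Table 2 gives a 96% stop probability at a true DLT rate of 40%.
- Section 10.6 lets the investigator or the company supporting the study discontinue at any time on reasonable grounds.
- The 19% and 44% figures need DLT rates of 20% to 30% at 25 mg/m² x 3 days and no use of the permitted lower cohorts. The hematologic DLT definition is demanding, and Section 2.4 describes 75 mg/m² x 7 days as well tolerated, though in MDS and without a TKI.

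All of this stands, and it keeps the point minor. It does not supply the missing condition. The reader has to infer what happens once -1 is exceeded, and the 9.3.2 boundary acts only after patients have been dosed.

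It is also tempting to read -4 as a slip for -3. Three mentions agree on -4, so Table 1 may equally lack a row. The documents do not settle which.

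**Conclusion.** The point holds as a minor inconsistency in the dose-selection and stopping wording. Two things follow from the text alone. The 75 x 3 days fallback is not conditioned on that level having been tested and not exceeded. The phase I stopping rule and the dose-reduction floor name a level that Table 1 does not contain.

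The size rests on assumed DLT rates. On the Section 9 ladder the toxic outcome without an MTD has probability 0.3% to 3.6% at low to moderate rates, and 19% to 44% only at high rates with no lower cohorts. With lower cohorts always opened, the chance that every level is exceeded is 0.7% or less in the three scenarios tabulated, and somewhat higher if the lowest levels are themselves assumed toxic. No sample size, power or analysis result is affected.

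**What to change.** 1. In 9.2.2 and 4.3, apply the 75 mg/m² x 3 days fallback only if that level was tested and did not exceed the MTD.
2. State that the study stops and phase II does not open if the lowest level tested is exceeded and no level meets the MTD definition.
3. Make the level in 4.2.4 (both mentions) and 4.5.4.5.1 agree with Table 1, either by using -3 or, if a -4 was intended, by adding that row.

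The fallback needs no separate clause for reaching the 18-patient cap, because condition 1 decides whether 75 is available. With level 1 as the top, every cap-first path has levels 0 and -1 exceeded and 75 either untested or exceeded, so the fallback does not apply. If levels 2 and 3 of Table 1 were used in phase I, the cap could be reached with level 1 tested and not exceeded, and the fallback would then rightly apply.

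The cost is one clause in two sections, one added sentence and a level number in three places. No patients or analysis work are added, and 18/36/48 and the 87% power stay as they are.

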9.3. Phase II

The primary endpoint for phase II portion is the decrease of transcript levels by at least one log (or undetectable transcript level) within 12 months. Including the 6 patients treated at the recommended phase II dose level in the phase I part, a total of 36 patients will be accrued.

9.3.1. **Efficacy Monitoring**

Since the efficacy of the drug will be assessed over a long period of time (12 months) and the accrual rate is relatively fast (1-2 patients per month), no formal futility monitoring rule will be applied. However, the PI and the study committee will meet regularly, and the study will be stopped early if consensus has been reached on any clear indications of poor efficacy of the drug.

9.3.2. **Toxicity Monitoring**

The method of Thall, Simon, and Estey will be used to perform interim safety monitoring [1]. The safety monitoring of the trial will be initiated after the first 6 patients have been evaluated, and then monitored continuously. The monitoring rule for toxicity is $P(\theta_E > 0.20 | \text{data}) > 0.90$, where θ_E is the proportion of any DLT (as defined in section 4.3.3), and is assumed to follow a non-informative prior of Beta (0.4, 1.6). Namely, the trial will be terminated if at any time during the study there is a more than 90% chance that the average rate of DLT is more than 20%. The stopping boundaries of the trial are ≥ 3 out of 6, ≥ 4 out of 7, ≥ 5 out of 10, ≥ 6 out of 14, ≥ 7 out of 18, ≥ 8 out of 22, ≥ 9 out of 26, ≥ 10 out of 30, ≥ 11 out of 34 patients experienced DLT.

Table 2: Operating characteristics of Safety Monitoring (based on 10000 simulations)				
True Probability	Stop Probability	Trial Sample Size Percentile		
		25%	50%	75%
0.10	0.02	36	36	36
0.20	0.25	36	36	36
0.30	0.69	6	17	36
0.40	0.96	6	8	16

All calculations were performed using Multc99.

9.4. **Statistical Methods**

Data analysis will be performed using SAS or S-plus, whichever is appropriate. All patients who receive at least one dose of therapy will be included in the primary efficacy and toxicity analysis. Patients who do not have molecular response and

withdraw within 12-months after initiation of treatment will be counted as failure in the primary efficacy analysis.

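### Six phase I patients enter the primary efficacy set without having to meet the phase II criteria, and Table 2 gives stopping probabilities for 36 unselected patients although those six have already passed phase I

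*Combined protocol and SAP*

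**What the plan says.** **Carry-over.** Section 9.2.2 defines the recommended dose: "MTD is defined as the highest dose level in which 6 patients have been treated and one or fewer patient experiences DLT". It has a fallback: "If MTD is not determined, the highest AZA level of 75" mg/m²/d for 3 days becomes the phase II dose. It then carries forward "The data from the 6 patients treated at the recommended phase II dose level". Section 9.3 repeats that, with these six "in the phase I part, a total of 36 patients will be accrued". Section 9.1 gives the overall size: "A total of 48 patients will be accrued at a rate of 1 to 2 patients per month".

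**Monitoring.** Section 9.3.2 stops the trial if the posterior probability of a DLT rate above 0.20 exceeds 0.90, under a Beta(0.4, 1.6) prior. "The safety monitoring of the trial will be initiated after the first 6 patients have been evaluated", and monitoring is continuous from there. The boundaries run from 3 of 6 to 11 "out of 34 patients experienced DLT". Table 2 gives stop probabilities by true DLT rate and does not mention phase I selection.

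**Population.** Objective 1.1.2 concerns patients in CCyR with minimal residual disease. For phase II, 3.1.3 requires CCyR, and 3.1.4 requires detectable transcripts plus at least one of 3.1.4.1 to 3.1.4.4. Section 3.1.3.1 lets phase I patients enter without CCyR if in chronic phase, and 3.1.4.5 admits them at any transcript level.

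**Analysis set.** Section 9.4: "All patients who receive at least one dose of therapy will be included in the primary efficacy and toxicity analysis".

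**The concern.** The efficacy question is about one population, and the rules for filling the analysis set admit another. No passage in 9.2.2, 9.3 or 9.4 asks whether a carried-over patient met the phase II criteria. Section 9.3 also accepts an undetectable transcript level as a response without requiring a detectable baseline, so a phase I patient already undetectable at entry would count as a success with no change at all.

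On safety, the people overseeing phase II will read Table 2 once the phase I result is known. The table leads them to expect that, at a true DLT rate of 0.30, 69% of trials stop and the median trial size is 17. The first six patients have by then been selected for few DLTs, so those expectations no longer describe what the rule will do.

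**Working it through.** **1. Do the six count in the monitoring?** New phase II patients: 36 − 6 = 30. With the phase I maximum of 18 (9.2.2), 18 + 30 = 48, which is the total in 9.1. The boundaries run to 34 and Table 2's sizes to 36, both above 30, so the six are counted.

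**2. Boundaries.** The boundary at n is the smallest x with P(θ > 0.20 | Beta(0.4 + x, 1.6 + n − x)) > 0.90. At n = 6, x = 2 gives 0.707 and x = 3 gives 0.914, so 3. At n = 10, x = 4 gives 0.895 and x = 5 gives 0.971, so 5. All nine listed boundaries are reproduced.

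**3. Table 2.** I used an exact forward recursion of the DLT count, with a look after every patient from 6 to 36, starting from no patients. The size percentiles match Table 2 (6/17/36 at 0.30, 6/8/16 at 0.40), except that at 0.20 the exact 25th percentile is 33 against 36 stated. That case is borderline, because the stop probability there is almost exactly 0.25. Looks only at the nine listed sizes give 0.018/0.177/0.590/0.911, which does not reproduce the table.

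**4. Given the phase I result.** Passing the 3+3 design with six treated means 0/3 then at most 1/3, or 1/3 then 0/3. That is exactly X₆ ≤ 1. The same recursion is started at n = 6 from that distribution.

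| True DLT rate | Table 2 | Exact, 36 unselected | Given ≤1 of 6 | Given 2 of 6 |
|---|---|---|---|---|
| 0.10 | 0.02 | 0.025 | 0.004 | 0.06 |
| 0.20 | 0.25 | 0.256 | 0.11 | 0.35 |
| 0.30 | 0.69 | 0.707 | 0.49 | 0.75 |
| 0.40 | 0.96 | 0.954 | 0.86 | 0.96 |

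Given at most 1 of 6, the size percentiles are 21/36/36 at 0.30 and 13/20/29 at 0.40. The earliest stop is patient 9 (1 + 3 = 4 DLTs, boundary 4). The last column is for a DLT added late (see the objection); the earliest stop is then patient 8 (2 + 2 = 4, boundary 4).

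**5. MTD not determined.** Section 9.2 does not ensure six patients at the fallback level. Assuming 0/3 there and then three unselected patients, the stop probabilities are 0.005/0.13/0.53/0.89.

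**6. Both phases together, for six patients at one dose level.** P(X₆ ≤ 1) = (1 − p)⁶ + 6p(1 − p)⁵. At p = 0.30 this is 0.118 + 0.303 = 0.420. Rejected in phase I or stopped later: 1 − 0.420 × (1 − 0.494) = 0.79. At the four rates: 0.12/0.42/0.79/0.97.

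**7. Efficacy.** Section 9.4 tests 5% against 20% with 36 patients, one-sided 5%, power 87%. With X binomial and a cut-off of 5, P(X ≥ 5 | 36, 0.20) = 0.873 and P(X ≥ 5 | 36, 0.05) = 0.032, so 87% is reproduced. With fewer qualifying patients, power at the same cut-off is 85.7% (35), 81.8% (33) and 74.5% (30, with one-sided alpha 1.6%). A cut-off of 4 of 30 restores power to 87.7%, but its alpha is 6.1%.

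**8. One automatic responder (illustration).** If one carried-over patient is undetectable at entry and is counted, four responders among the other 35 suffice. P(X ≥ 4 | 35, 0.05) = 1 − (0.166 + 0.306 + 0.274 + 0.158) = 0.096, against 0.032 in step 7.

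**The case against.** **Table 2 claims nothing about phase I.** It lists results by fixed true probability and, read as unconditional, is approximately right. This stands: what is missing is a label and a companion table. A reader might infer that the stopping rule is too weak. The documents do not support that. The boundaries follow from the stated prior and threshold, and phase I has already screened the dose, so at 0.30 about 0.79 are rejected or stopped over both phases, against 0.69 in Table 2.

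**An early stop is not strictly ruled out.** It is tempting to say that patient 9 is the earliest possible stop in every case. But 4.2.3.4 requires cytopenia lasting 6 weeks (8 with a normocellular marrow), while 4.2.1 and 4.2.3.1 work with 4 weeks. A hematologic DLT in the six could therefore be established after the MTD decision. With 2 of 6 the probabilities come back close to Table 2 or above it. This stands as a limit on the conditional figures.

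**The median of 17 is over all trials.** It does not mean that half of the stopped trials stop by patient 17; among stopped trials the exact median is 12.

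**Pooling is openly planned, and 9.1 describes the whole trial as CCyR with minimal residual disease.** Planned pooling is acceptable in itself. But the sentence in 9.1 is a description, and it cannot override the express phase I exemptions in 3.1.3.1 and 3.1.4.5. All six may in fact qualify, and the 5% and 87% figures would then be unaffected by the carry-over.

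**The fall to 74.5% could be read as the damage done.** It is not. It is the cost of excluding all six. The bias from keeping non-qualifying patients cannot be sized from the documents, because neither their number nor their type is given.

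**Conclusion.** The point holds in two parts and should be fixed.

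**Efficacy (the main part).** As written, between 0 and 6 of the 36 patients, at most one sixth, may lie outside the population of objective 1.1.2, and one already undetectable at entry would literally satisfy 9.3. Step 8 shows that one such patient is enough to matter at a cut-off of 5. The direction for other non-qualifying patients, such as those without CCyR, is not determined. The power figures assume that cut-off, which reproduces the stated 87% but does not appear in the plan.

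**Safety table.** Table 2 is an unlabelled unconditional table. Given at most 1 DLT in the six at the MTD decision, the chance of stopping at a true rate of 0.30 is 0.49 rather than 0.69, and the median size is 36 rather than 17. This is an error in describing the phase II monitoring, not a fault in the rule. It rests on the six being the first six monitored, a constant DLT rate, a look after every patient and no late DLT.

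**What to change.** 1. In 9.2.2, 9.3 and 9.4, include in the primary efficacy set only carried-over patients who at entry met 3.1.3 and 3.1.4 as required for phase II. Keep the others for safety. State the efficacy cut-off and restate power for the number left.
2. Use one endpoint definition in 9.3 and 6.1, in which undetectable counts only from a detectable pre-AZA baseline. Section 6.1 cannot simply be copied: its baseline refers to vaccination, and it asks for more than a one-log reduction where 9.3 asks for at least one log. Reconcile these at the same time.
3. In 9.3.2, state that the six count, label Table 2 unconditional, and add the table conditional on at most 1 of 6, with a note on late hematologic DLTs.
4. Give the MTD-not-determined route with its assumption. Table 1 in section 4.2 has levels above 75 mg/m²/d for 3 days, while the table in 9.2 ends there; the passages must be reconciled.

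**Cost.** Wording, one recalculation and an entry check on six patients. The boundaries do not change. Power falls to 74.5% at worst. Replacing non-qualifying patients instead would add at most 6 (48 to 54, about 3 to 6 months at 1 to 2 per month). If the six still counted for safety, it would also need boundaries beyond 36.
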